- If the patient passes after the completion of T1 but prior to the completion of T2, the patient/family dyad will be withdrawn from the study.
- If the patient passes after the completion of T1 and T2 but prior to T3 completion, the patient /family dyad will remain eligible to continue study participation; however, the study team will be mindful and sensitive regarding approach and may skip T3. It is not considered a deviation if the family completes T3 prior to the study team enabling the "skip" option within ICUconnect.

• If the patient passes after the completion of T1, T2, and T3 but prior to completion of T4, the study team may wait 1 month before asking the family to complete the fourth and final study survey. It is not considered a deviation if the family completes T4 1 month late.

In regards to survey completion, it is understood, given the nature of the study design (self-directed participant survey completion), that surveys may not be completed in the specified protocol windows. The study team will provide participant education at the time of consent regarding the importance of completing surveys in a timely manner. In addition, the study team will follow-up with participants (patient /family dyads and clinicians) via phone, email, and in-person to complete study surveys and/or family meetings, as applicable.

The study consists of the following statuses for patient/family dyads:

- Consented: an individual(s) who meets all eligibility criteria and has voluntarily agreed to participate in the study (RCT or ancillary).
- Enrolled: an individual whom, after consent is obtained, completes the first survey.
 - Nte: if a participant is enrolled in the RCT study and receives a NEST score of < 15, he/she
 is deemed a screen failure and is therefore no longer enrolled. If a participant is enrolled in
 the ancillary study, he/she does not need to meet a NEST threshold for enrollment.
- Screen Fail: any participant who is enrolled into the RCT and receives a score of < 15.
- Withdrawn by PI: any participant who does not comply with study specific requirements (i.e. such as timely completion of study surveys, specifically T1 and/or T2) or is found to be by the principal investigator no longer appropriate for this study due to current state of being (physical, mental and /or emotional).
- Withdrawn by Self: voluntary withdraw of participant from study for any reason.
- Completed: any participant (RCT or ancillary) who completes 75% of study visits.

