The study consists of the following statuses for clinicians:

- Consented: an individual clinician who is on service at the time of the eligible patient/family dyad admission and has agreed to voluntarily consent to the study.
- Randomized: a clinician who has been randomized to one of the two study arms:
 - Interventin: a clinician wh receives the patient/family dyad T1 and T2 survey results, conducts a family meeting to discuss results, and completes a clinician survey post family meeting and survey results review.
 - Cntrol: a clinician wh neither receives patient/family dyad T1 and T2 surveys nor conducts a family meeting to discuss results.

Given the nature of the targeted population under study and that the goal of this study is to address unmet needs and racial disparities among ICU family members, we do not anticipate adverse events and /or serious adverse events. However, it is possible that the patient/family dyad could become distressed in an ICU setting, especially as the patient becomes more ill and/or dies. As a result, the study team will monitor, document and report suicidal ideation (SI) as an Adverse Event (AE). The monitoring of SI is operationalized by the participant responding to one of the survey questions (PHQ-9; #9: Thoughts that you would be better off dead or of hurting yourself in some way). An automated alert is triggered and an email is sent to the Principal Investigator, the Study Manager, and the Clinical Research Coordinators. The PI will be the primary responsible party for addressing the SI alert; however, the Study Manager may also serve in the PI's absence. Both are trained on the Columbia Suicide Severity Rating Scale (C-SSRS).

A serious adverse event (SAE) for this trial would include a suicide attempt. Again, given the nature of the targeted population under study, it is not unexpected that the patient would experience hospitalization and subsequent ICU admission (or even repeat hospitalization, if discharged), therefore, the study will not document and/or report hospitalizations and/or deaths for the patients. However, if the enrolled family member and/or clinician were to be hospitalized and/or pass away, the study team would consider this an SAE and would document and report appropriately.

All protocol defined AEs and SAEs will be reported to the appropriate agencies (NIH) and the institutional review board, as appropriate and in line with guidelines and policies.

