 - b. If a patient is intubated on the day of eligibility but then subsequently extubated the same day, the patient remains eligible for the study as long as consent and T1 are completed within 8 hours of extubation.
- 3. Death must not be imminent (< 24 hours)

Inclusion Criteria (Family Members, Pre-Consent)

- 1. One family member per patient is eligible.
- 2. The family member must be \geq 18 years old.
- 3. The family member must be self-described as the individual (related or unrelated) who provides the most support and with whom the patient has a significant relationship.

Inclusion Criteria (Clinician, Pre-Consent)

1. Patients' bedside ICU attending physicians on the day of family consent are eligible.

Exclusion Criteria (Patients, Pre-Consent)

- 1. Patients who are admitted to an ICU at the index hospital >14 days will be ineligible for participation.
- 2. Patients who are on comfort care or are planned to undergo withdrawal of treatment within the following 48 hours of enrollment will be excluded.
- Prisoners
- 4. Patients who have no known family or surrogate.
- 5. Patients who are transferred to a non-study ICU or non-study clinician will be excluded if they are enrolled into the RCT only.

Exclusion Criteria (Family Members, Pre-Consent)

- 1. Family members will be excluded if they lack English fluency or have other limiting factors that inhibit their ability to use the app (e.g. literacy, blindness, etc).
- 2. Family members will be excluded if they are not directly involved in decision making, are unreachable or unavailable.
- 3. Family members will be excluded if they are <18 years of age.
- 4. Family members will be excluded if they are unable to consent (e.g., dementia, cognitive impairment).
- 5. Prisoners.
- 6. For the RCT only: family members who self-identify as Hispanic and/or self-identify most with a racial group other than White or Black will be excluded.
 - a. Ethnic and racial exclusions do not apply to the ancillary study.

Exclusion Criteria (Patient/Family Dyad Post-Consent)

- 1. Patient dies before T2 is completed.
- 2. Family members will be excluded from the RCT, but not the ancillary study, who have a very low need burden (NEST < 15) after the completion of T1.
- 3. For the primary RCT, participants are also excluded if the randomized physician leaves ICU service or is replaced by a non-participating ICU physician < 2 calendar days after family completes T1.

For Aim 4 RCT (or Aim 3 Ancillary Study) Only:

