Aim 2's RCT will be supervised by a single independent central DSMB due to its interventional nature. The DSMB will include professionals with significant experience in clinical trials, mind-body interventions, and biostatistics who are not directly involved in the study, its interpretation, or any study institution. DSMB members will be chosen with the assistance and approval of the NIH. The main responsibilities of the DSMB will be to (a) assess for the presence of potential harms and unintended consequences of the intervention, (b) ensure the validity and integrity of the data, and (c) make recommendations to the NIH about whether the study should be continued without modification, continued with modification, or terminated. The initial DSMB meeting will occur before the initiation of subject enrollment for the purpose of updating members on the study, ensuring agreement on the review process, and establishing the review methodology and procedures. The first DSMB data review will then occur either after the first 10 patients (5 per treatment group) have been enrolled or enrollment has occurred for 3 months, whichever is observed first. Thereafter, the DSMB will review cleaned data pulled from the RedCap database system every six months during enrollment and will prepare a report with any recommendations within the following month. While this is an intensive DSMB engagement schedule, the short enrollment period will demand greater oversight.

The specific study functions and outcomes that the DSMB will review at each meeting include: dropout rate, randomization rate, NEST, PHQ-9, GAD-7, and Post-Traumatic Stress Scale (PTSS) scores. The primary safety measures will be Adverse Events reports and post-intervention PHQ-9 scores. Other items reviewed by the DSMB at each meeting will include: (a) data quality, completeness, and timeliness; (b) performance of the Duke center; (c) adequacy of compliance with goals for recruitment and retention, including women and minorities; (d) protocol adherence; and (e) presence of factors that could adversely affect study outcome or compromise data confidentiality.

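### Families bereaved between T1 and T2 are withdrawn, so they have no post-intervention PHQ-9, although that score is a primary safety measure and the intervention meeting falls in the same interval

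*Protocol*

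**What the plan says.** **Death during participation (Protocol, Design & Procedures).** If the patient dies after T1 but "prior to the completion of T2, the patient/family dyad will be withdrawn from the study". Selection of Subjects repeats this as a post-consent exclusion: "Patient dies before T2 is completed". Later deaths are handled differently. If the patient dies between T2 and T3, the dyad stays in and the team "will be mindful and sensitive regarding approach and may skip T3". If the patient dies between T3 and T4, the team "may wait 1 month before asking the family to complete the fourth and final study survey". In both later cases T4 is still due.

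**Why and how suicidal ideation is monitored (same section).** The stated reason is that "it is possible that the patient/family dyad could become distressed in an ICU setting, especially as the patient becomes more ill and/or dies". The method is a survey answer: "The monitoring of SI is operationalized by the participant responding to one of the survey questions", namely PHQ-9 item 9.

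**Timing of the intervention (same section).** The intervention clinician's family meeting takes place after T1 and before T2.

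**What the DSMB relies on (Data & Safety Monitoring).** "The primary safety measures will be Adverse Events reports and post-intervention PHQ-9 scores". A statistically significant PHQ-9 increase in the intervention group is a ground on which the DSMB may recommend stopping the trial.

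**The concern.** The participant who is surveyed and monitored is the living family member, not the patient. The patient's death before T2 removes that person from the study, and the score named as a primary safety measure goes with them. Patient death is part of the protocol's own reason for watching for suicidal ideation, and the interval concerned is the one in which the intervention is delivered.

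If a needs-focused meeting shortly before a death did harm some relatives, the PHQ-9 comparison could not show it, because those relatives would have no score after the meeting. The adverse-event count is also weakened. The listed serious events for a family member (suicide attempt, hospitalisation, death) become known only through some contact, and none is scheduled after withdrawal.

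**Working it through.** The plan states no figure on this point, so there is none to reproduce. The check sets the rules side by side and then sizes the gap.

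**1. Which surveys remain, by time of death**

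| Patient dies | Status of family member | Surveys still due |
|---|---|---|
| After T1, before T2 completed | Withdrawn | None |
| After T2, before T3 | Stays in | T3 (may be skipped), T4 |
| After T3, before T4 | Stays in | T4 (may be a month late) |

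Only the first row leaves no later survey.

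**2. Does the result depend on which surveys carry the PHQ-9?** The documents do not list its time points. The SAP calls it a longitudinal outcome without giving times. The ancillary analysis text names PHQ-9 scores at T4. T3 is described only as a mini survey. For the first row this does not matter: T2, T3 and T4 all fall after withdrawal, so no post-intervention PHQ-9 can exist whichever of them carries it.

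**3. Does the meeting precede the loss?** T2 is due 3 days after T1, with 1 day's allowance. The meeting and the withdrawal rule occupy the same interval, so the sequence T1, meeting, death, withdrawal is possible under the protocol's own schedule.

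**4. Is there another route?** The Risk/Benefit section lets staff activate the suicidality plan after a worrying in-person or telephone contact. The follow-up contacts in Design & Procedures are for completing surveys and meetings. Neither section schedules contact with a withdrawn family.

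**5. Size**

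Inputs: 240 dyads (Design & Procedures) or 160 families (power text); equal arms (assumed); share *p* of patients dying between T1 and T2 (not given; 2-10% assumed). The protocol says only that death during participation is highly likely.

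Intervention families affected = (N/2) × *p*:

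- N = 240: 120 × 0.02 = 2.4; 120 × 0.05 = 6; 120 × 0.10 = 12.
- N = 160: 80 × 0.02 = 1.6; 80 × 0.05 = 4; 80 × 0.10 = 8.

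Both arms together (N × *p*):

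- N = 240: 4.8 at 2%, 24 at 10%.
- N = 160: 3.2 at 2%, 16 at 10%.

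The intervention-arm counts include every death in the interval, so they are upper bounds for families who had already had the meeting.

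**The case against.** The strongest reply is that early withdrawal is a deliberate, humane choice in a minimal-risk survey study, and that the same rule applies in both arms. The plan is careful with bereaved families elsewhere, too. That explains caution in making contact. It does not explain why a family bereaved just before T2 has no safety follow-up while one bereaved just after T2 is still asked for T4. Applying the rule to both arms does not recover the missing scores.

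Several other objections stand and limit the point:

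- **Other signals exist.** Staff concern is a second route to detecting suicidal ideation, and the DSMB reviews dropout at each meeting, so uneven loss between arms would be partly visible. Neither supplies a PHQ-9 score.
- **The count is soft.** The death rate is assumed. Patients expected to die within 24 hours, on comfort care, or with withdrawal of treatment planned within 48 hours are excluded, which should lower early deaths. Because death before T2 is a post-consent exclusion, and about 320 dyads are to be consented so that 240 meet all criteria, these dyads may not be counted within the 240 at all.
- **T4 comes late.** A T4 score about three months after T1 would not monitor suicidal ideation at the time of the death.

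A reader might also infer that the protocol calls the patient's death the moment of highest suicide risk, or that monitoring lapses after a death at any time. The documents support neither. The protocol links death to distress and ranks no moment for suicide risk. The T3 skip and the T4 wait are optional, and T4 remains due. T3 is not stated to carry the PHQ-9, so skipping it may remove no suicidal-ideation item. Most of the interval between T3 and T4 is the ordinary schedule for every family.

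**Conclusion.** The point holds for one group: families whose patient dies after T1 and before T2 is completed. Their post-intervention PHQ-9 is missing by design, and nothing is scheduled through which an adverse event would be learned of. The PHQ-9 results reviewed by the DSMB therefore describe only families whose patient survived to T2, a subset formed after randomisation.

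Under the assumed 2-10% death share and equal arms, this is about 2-12 of 120 intervention families, or about 2-8 of 80. It is subject to whether such dyads count within the enrolled total. The gap in the rules is there whatever the rate; only its size depends on the assumption.

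This is a moderate weakness in safety data collection that should be corrected. It is not evidence that the intervention causes harm, and it does not bear on whether these dyads belong in the T1-T2 NEST analysis.

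**What to change.** Reconcile the death rules and adverse-event text in Design & Procedures, the post-consent exclusions in Selection of Subjects, and Data & Safety Monitoring, so that:

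- death before T2 ends the needs surveys and keeps the dyad out of the T1-T2 NEST analysis, as now, but the family member stays in for safety data collection;
- the existing T4 survey is offered to these families, expressly as voluntary, with the optional one-month wait that the protocol allows after a later death (that rule contains no opt-out wording, so the voluntary terms must be written in);
- their adverse and serious adverse events are counted by arm;
- they appear as a separate row in the DSMB's PHQ-9 table;
- the surveys that carry the PHQ-9 are listed.

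This changes data collection and tabulation only; the suicidality response plan is untouched. It would fill the gap in the arm comparison. It would not provide monitoring at the time of the death.

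**Cost.** One amendment, one optional contact with a bereaved relative (which the plan already accepts for deaths after T2), and $20 per T4 survey. Under the assumed rates that is about 5-24 surveys across both arms, or $100-480, with N = 240, and about 3-16 surveys, or $60-320, with N = 160.

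**If follow-up has closed.** The SAP is written in the past tense, so this may be the case. The sponsor can then report the number of withdrawals for death before T2 by arm, and state that the PHQ-9 results exclude those families.

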Assuming that a participant receives a NEST score of \geq 15, regardless of clinician randomization, the participant will continue with the following study procedures:

- Survey 2 (T2) to be completed within 3 days (0/+1 day) of T1 completion.
- Survey 3 (T3) to be completed within 7 days (0/+3 days) of T1 completion
- Survey 4 (T4) to be completed within 3 months (90 days, 0/+3 days) of T1 completion.

Should a participant receive a NEST score of \geq 15 and be randomized to an intervention clinician, the participant will be contacted by the intervention clinician have a family meeting. Family meetings are to occur after the completion of T1 but prior to the completion of T2. Given the short timeframe between T1 and T2, the clinician can conduct the family meeting in a variety of settings: in the ICU at bedside, in a private conference room and/or location within the waiting room (at the choice of the participant), and/or over the phone.

In conjunction with Aims 2 and 3 of the RCT, the study team will simultaneously enroll patient/family dyads into the ancillary study. The ancillary study will include a total of 250 enrolled patient/family dyads. Eligible participants will be approached for consent at the time of the ICU admission. Participants enrolled into the ancillary study will be those participants whose current attending clinician is not enrolled in the RCT and/or their identified primary race and ethnicity is something other than White or African American /Black and Non-Hispanic. Participants enrolled in the ancillary study, like the RCT, must meet study eligibility criteria.

Participants enrolled into the ancillary study will complete an ICUconnect profile and then be asked to complete the following surveys:

- Survey 1 (T1) to be completed within 24 hours of consent.
- Survey 2 (T2) to be completed within 3 days (0/+1 day) of T1 completion.
- Survey 3 (T3) to be completed within 7 days (0/+3 days) of T1 completion
- Survey 4 (T4) to be completed within 3 months (90 days, 0/+3 days) of T1 completion.

Given that the targeted patient population involves individuals who are seriously ill and/or injured, the study team expects that there is a high likelihood that death could occur while the patient/family dyad's participation is ongoing. Should a patient pass away while study participation is ongoing, the following will occur:

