Our Suicidality Response Plan can be activated in two main ways. First, study staff (coordinators, investigators, PI) may have in-person or telephone interactions that concern them. Second, the study data system will automatically detect any endorsement of the PHQ-9's suicidality item, sending an alert email in real time to the Study Manager and the PI. An example of this alert system in the context of using the Hospital Anxiety and Depression Scale (HADS) questionnaire in the CSTEP RCT is shown in the screenshot below.

If the participant is deemed to be at high risk based on direct interaction or the PHQ-9 item response, then the PI and study manager will be notified immediately. Using the C-SSRS, the PI will then help to assess the participant to determine if they endorse active suicidal ideation. The PI will also determine of the participant is currently being treated by a mental health professional.

If the patient is deemed not to be actively suicidal, they will be given a list of local mental health resources as follows:

Duke: Call Emergency Psychiatry at [name] or [name], available 24 hours a day, 7 days a week.

Backup: The National Suicide Prevention Lifeline - [name] is a free, 24-hour hotline available to anyone in suicidal crisis or emotional distress.

If the participant is considered to be actively suicidal then at least one of the following plans will be followed depending on the location of the participant for each of the following situations:

- Situation 1. If the participant is with one of the study personal:
 - a. The study personnel will notify the PI immediately
- b. The study personnel will either physically walk the subject to the emergency department, or call a Psychiatric Emergency services number.
- Situation 2. If the participant is on the telephone:
 - a. The study personnel will notify the PI immediately.
 - b. The study personnel will stay on the telephone with the subject participant.
- c. The study personnel will immediately contact 911 to initiate an on-site rescue if such action is clinically indicated.
- d. The study personnel will stay on the telephone with the subject until EMS services have contacted the participant.
- Situation 3. If there are any active suicidal concerns in any of the surveys (e.g., PHQ-9 above):
 - a. The study data system will notify the PI and Study Manager immediately.
 - b. Next, the study personnel will contact the participant by telephone.

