During the review process, formal statistical tests for examining the differences in Adverse Event or outcome rates between study groups may be performed under DSMB supervision if requested. However, this is unlikely given the exploratory pilot study design. For differences in study dropout rates, appropriate changes to the protocol will be made by investigator consensus after DSMB member input. Additionally, the DSMB may request a formal statistical assessment if a suspicious increase in PHQ-9 score is observed in either group. If the intervention group is found to have either a statistically significant increase in PHQ-9 score, the DSMB scope of action will include recommendation for cessation of the trial. [name], the biostatistician, will oversee any DSMB statistical requests and interpretations. Any protocol changes, as well as any adverse events, will also be reported to the Institutional Review Boards of all study sites, as well as to the NIH.

Privacy, Data Storage & Confidentiality

• Complete the Privacy and Confidentiality section of the iRIS submission form.

Describe Role of External Personnel:

N/A

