NCT03506438

Full Title: Addressing Palliative Care Needs Among Intensive Care Unit Family Members

Document Date: 04/28/2021

Statistical Analysis Plan (Pro00090202)

Statistical Analysis Plan

The goal of the primary hypothesis was to determine the efficacy of the ICUconnect intervention versus usual care on reduction in unmet needs from T1 to T2. Unmet needs were assessed at T1, T2, and T3 with the total NEST score, a continuous, normally distributed measure. Because each family member was surveyed at multiple time points and the same ICU physician saw several patients, outcome variable measurements were not be independent. Therefore hierarchical linear models fit via PROC MIXED in SAS 9.4 (Cary, NC) were used as the primary analytic strategy they appropriately accounted for the multiple types of correlation inherent in our study design. The other continuous, longitudinal outcomes included: PHQ-9, GAD-7, PTSS, and QOC; hierarchical linear models were also used to estimate the treatment effect over time for these outcomes. The binary outcomes of goal concordant care and IPC (dichotomized due to ceiling effects) were analyzed via generalized linear models with a logit link and fit with generalized estimating equations (PROC GENMOD in SAS, 9.4). Finally, treatment group differences in hospital and ICU length of stay were examined with a Wilcoxon test.

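### Suicidal ideation already present at T1 enters the adverse-event counts on the same footing as later ideation; for tabulation by arm it should be shown separately as baseline status (minor)

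*Protocol*

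**What the plan says.** **Event definition.** Protocol, Design & Procedures: "the study team will monitor, document and report suicidal ideation (SI) as an Adverse Event (AE". The same paragraph adds that "The monitoring of SI is operationalized by the participant responding to one of the survey questions", namely PHQ-9 item 9. No survey is named, and nothing requires the ideation to be new or worse. In the Risk/Benefit Assessment, "the study data system will automatically detect any endorsement of the PHQ-9's suicidality item", again with no survey excluded.

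**Timing of exposure.** Under Design & Procedures, "Family meetings are to occur after the completion of T1 but prior to the completion of T2". Under Study Interventions, the intervention clinician receives the T1 results once T1 is complete. Nothing differs between the arms for a family until T1 is done.

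**Safety review.** Data & Safety Monitoring: "The primary safety measures will be Adverse Events reports and post-intervention PHQ-9 scores". That section also says that "formal statistical tests for examining the differences in Adverse Event or outcome rates between study groups may be performed under DSMB supervision if requested", and then calls such tests unlikely.

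**PHQ-9 schedule.** No section lists the contents of each survey. The SAP says "The other continuous, longitudinal outcomes included: PHQ-9, GAD-7, PTSS, and QOC", and Data & Safety Monitoring speaks of an increase in PHQ-9 score.

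**The concern.** Ideation endorsed at T1 cannot be an effect of the clinician's review of results or of the family meeting, because both come later. As written, it is recorded as an adverse event under the same definition as ideation that first appears after the meeting. The plan limits the PHQ-9 score to post-intervention values but sets no such limit on the adverse-event measure beside it.

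Ideation is the only non-serious adverse event that the protocol specifies, so T1 cases could make up much of the adverse-event report. Two things follow when counts are read by arm. Baseline cases common to both arms shrink the ratio and add variability. A chance or recruitment imbalance at T1 can also offset a real difference or imitate one.

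**Working it through.** The documents give no ideation rate, adverse-event rate or safety power, so there is no figure of theirs to reproduce. What follows is an illustration.

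**Step 1: is item 9 asked at T1?** Three indications support it. PHQ-9 is a longitudinal outcome in the SAP; the DSMB looks for an increase in it; and the qualifier post-intervention implies an earlier value. No sentence says so outright. It is a strong inference.

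**Step 2: inputs.**
- n = 80 families per arm, from the power section (160 families, two arms).
- Two-sided 0.05, which the protocol states for its efficacy hypotheses and is borrowed here.
- Assumed: T1 prevalence b = 3%, 6% or 10%, equal in both arms.
- Assumed: risk of new ideation among families negative at T1, c = 2% (control) and i = 12% (intervention).
- Each family counts once; worsening among T1-positive families is ignored; clustering by physician is ignored.

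**Step 3: formulas.** With T1 cases counted, the risks are b + (1 − b)c and b + (1 − b)i. The ratio is their quotient. The difference is (1 − b)(i − c), so it shrinks only by the factor (1 − b). For b = 3%:
- control 0.03 + 0.97 × 0.02 = 0.0494
- intervention 0.03 + 0.97 × 0.12 = 0.1464
- ratio 0.1464 / 0.0494 = 2.96; difference 0.0970

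**Step 4: results.** Power is for Fisher's exact test, by enumeration. With T1 cases excluded, the event risks are (1 − b)c and (1 − b)i out of 80. Restricting the denominator to the families at risk gives the same power to within half a percentage point.

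| T1 prevalence | Risks with T1 counted | Ratio (6.0 for new ideation) | Difference (10.0 points for new ideation) | Power, T1 counted | Power, T1 excluded |
|---|---|---|---|---|---|
| 3% | 4.9% v 14.6% | 3.0 | 9.7 points | 46% | 60% |
| 6% | 7.9% v 17.3% | 2.2 | 9.4 points | 36% | 58% |
| 10% | 11.8% v 20.8% | 1.8 | 9.0 points | 27% | 55% |

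The comparator is the last column. Power of 62% would apply only if no family were positive at T1.

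**Step 5: other assumed rates.** With 2% versus 8%, the ratio falls from 4.0 to 2.2, 1.7 or 1.5, and power is 19%, 15% or 11% with T1 counted against about 25%, 23% or 21% with T1 excluded. With 3% versus 9%, the ratio falls from 3.0 to 1.98 at b = 3% and 1.43 at b = 10%. Ratios and differences do not depend on n. Power does, and Design & Procedures gives a different target of 240 dyads, about 120 per arm.

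**Step 6: chance imbalance.** Take two independent binomial counts with n = 80 and equal prevalence. The T1 counts differ by three or more between arms with probability 24% at b = 3% and 40% at b = 6%.

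**The case against.** The case on the other side is substantial.

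- **PHQ-9 at T1 is not stated.** Correct. If item 9 is not in T1, one sentence saying so closes the point.
- **No adverse-event test by arm is planned.** A reader might infer that the DSMB depends on such a comparison and that its power is being lost. The protocol makes formal tests available on request and calls them unlikely, so the power figures describe an optional analysis. What remains is that the reports are reviewed in any case, and a count that mixes baseline and later ideation can mislead without a test.
- **Other safeguards exist.** A reader might infer that harm would be hidden. The post-intervention PHQ-9 score is the other primary safety measure and itself contains item 9. The DSMB also reviews GAD-7 and PTSS scores. The protocol ties a recommendation to stop the trial to a statistically significant PHQ-9 increase, not to an adverse-event ratio.
- **The relatedness rule helps.** An event with no temporal relationship to the intervention is classed as not related, and T1 ideation fits that class. But the rule labels single events; it does not remove them from counts by arm or require tables by survey.
- **The absolute excess survives.** True: 10.0 points becomes 9.7 to 9.0. The loss is in the ratio and in precision.
- **Reporting all ideation is a cautious choice, and the DSMB sets its review methods at its first meeting.** Both are fair, and the fix respects both: only the tabulation changes.

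**Conclusion.** The point holds as a minor one. Followed as written, the definition puts ideation that precedes any arm-specific exposure into one of the two primary safety measures, while the companion measure is restricted to post-intervention values. In any reading by arm, this pulls the ratio toward 1 and adds noise: under the lead assumptions, from 6.0 to between 3.0 and 1.8, with Fisher power of 46% to 27% instead of about 60% to 55%. The direction does not depend on the assumed rates, given similar T1 prevalence in the two arms and a higher risk of new ideation under intervention. The size does, and the documents do not fix it.

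The conclusion rests on item 9 being in T1, which is inferred. It does not extend to a claim that the safety monitoring would miss harm. The documents do not support that, given the post-intervention PHQ-9 review, the relatedness label and the near-constant risk difference.

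**What to change.** 1. In Design & Procedures, state which surveys carry PHQ-9 item 9.
2. For DSMB tables by arm, count ideation that is first endorsed after T1, or endorsed after T1 at a higher level than at T1. Show T1 endorsement by arm in a separate column as baseline status.
3. Leave the alert, the response plan and institutional reporting unchanged at every survey, T1 included. The change concerns classification and tabulation only.

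Cost: a sentence or two in the protocol and one more column in the DSMB table. No new data are needed. The small downside is that the DSMB reads two counts in place of one.
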